2. STUDY OBJECTIVES

The primary objective is:

 To evaluate the efficacy of BEM compared with placebo in reducing all-cause hospitalization or all-cause death in COVID-19 outpatients receiving only supportive care.

The secondary objectives are:

- To evaluate the efficacy of BEM compared with placebo on:
 - COVID-19 related hospitalization or all-cause death through Day 29
 - All-cause death through Day 29 and Day 60
 - COVID-19-related complications (eg., death, hospitalization, radiologically confirmed pneumonia, acute respiratory failure, sepsis, coagulopathy, pericarditis/myocarditis, cardiac failure) through Day 29
 - COVID-19-related medically attended visits (hospitalization, emergency room (ER) visit, urgent care visit, physician's office visit, or telemedicine visit) or all-cause death through Day 29 and Day 60
 - COVID-19 symptom relapse
- To evaluate the antiviral activity of BEM compared with placebo on viral load rebound
- To evaluate the safety of BEM compared with placebo

The exploratory objectives are

- To evaluate the efficacy of BEM compared with placebo on:
 - Alleviation or improvement of individual COVID-19 symptoms
 - Return to usual (pre-COVID-19) health
 - Requirement for post-randomization rescue therapy
 - The antiviral activity of BEM compared with placebo
- To assess plasma concentrations of AT-511 (free base form of AT-527 [BEM]) and its metabolites from sparse PK sampling at steady-state

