3.1.3. Exploratory Objectives

The exploratory objectives are

- To evaluate the efficacy of BEM compared with placebo on:
 - Sustained alleviation or improvement of COVID-19 symptoms
 - Return to usual (pre-COVID-19) health
 - Requirement for post-randomization rescue therapy
 - The antiviral activity of BEM compared with placebo
- To assess plasma concentrations of AT-511 (free base form of AT-527 [BEM]) and its metabolites from sparse PK sampling at steady-state.

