6.1. General Summary Table and Individual Subject Data Listing Considerations

Unless otherwise specified, continuous variables will be summarized by using the number of non-missing observations, arithmetic mean, standard deviation (SD), minimum, first quartile, median, third quartile and maximum values as summary statistics; categorical variables will be summarized by using the frequency count and the percentage of subjects in each category as summary statistics. Descriptive summaries will be tabulated by treatment group.

When a summary tabulates the number of subjects, subjects will only be counted once for a category (e.g., a particular adverse event type, a particular adverse event term, a particular concomitant medication) unless otherwise specified.

All statistical tests will be performed at a 0.025 significance level using one-sided tests, unless otherwise noted. Statistical tests will use stratification factors (age and region) according to randomization. Stratification factors may need to be removed or have their levels combined so that low or zero counts in one stratum do not invalidate relevant statistical tests.

Unless otherwise specified, all efficacy and virology analyses will be performed on the modified intent-to-treat (mITT) analysis populations for each stratum. All safety analyses, demographics, and baseline characteristics will be performed on the safety population. Refer to Section 6.5 for details on analysis population definitions.

All Safety, Efficacy, and Tolerability data will be listed. In cases where additional information may be helpful, considerations for listings will be noted in this document.

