7.4. Demographic and Baseline Characteristics

To review treatment group comparability within the study, a number of variables collected at baseline will be presented by treatment groups on the mITT-S, mITT-C and safety analysis populations. No statistical comparisons will be made on these characteristics.

Demographic variables to be summarized include:

- Age
- Age group $(18-49, 50-64, 65 79, \ge 80)$
- Sex
- Race
- Ethnicity
- Country
- Region
- Weight
- Body mass index (BMI).

Baseline Disease Characteristics to be summarized include:

- SARS-CoV-2 RT-PCR viral load at baseline
- SARS-CoV-2 IgG seropositive status at baseline
- Presence of individual high-risk factors (age groups, obesity by age groups, diabetes by age groups, cardiovascular disease by age groups, chronic lung disease by age groups, immunocompromised or immunosuppressed by age groups, other high-risk conditions by age groups)
- Time from symptom onset to study treatment in days
- COVID-19 vaccination status
- Baseline lineage

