Time to cessation of SARS-CoV-2 viral shedding by RT-qPCR Time to cessation of SARS-CoV-2 viral shedding will be explored using Kaplan-Meier analysis in two ways: 1) time from first detectable observation of SARS-CoV-2 to the time of the first observation with non-detectable SARS-CoV-2; 2) time from first detectable observation of SARS-CoV-2 to the time of first non-detectable observation of SARS-CoV-2 where the non-detectable status is sustained through Day 29. Where a subject does not meet the cessation endpoint, time to cessation will be censored at the time of the last viral RNA assessment. In cases where the result of SARS-CoV-2 testing is reported as inconclusive, the following rules will be applied:

- If inconclusive observation happens before the first non-detectable observation and all follow up observations are non-detectable, time to sustained cessation is time to the first non-detectable observation.
- If inconclusive observation happens between two non-detectable observations, it is treated the same as non-detectable observation.
- If inconclusive observations happen in the last assessments, time to cessation will be censored at the time of last non-inconclusive assessment.

Change from baseline in amount of severe acute respiratory syndrome coronavirus-2 (SARS-CoV-2) viral RNA as measured by reverse transcription quantitative polymerase chain reaction (RTqPCR) over time and Proportion of subjects negative for SARS-CoV-2 viral RNA by RT-qPCR over time

SARS-CoV-2 viral RNA (and change from baseline) will be summarized at each scheduled time point by descriptive statistics on log_{10} viral load and tabulation of the number and percentage of subjects with non-detectable virus. The analysis will also be carried on subgroups of baseline viral load (<median, >=median).

Area under the curve (AUC) in the amount of SARS-CoV-2 viral RNA as measured by RTqPCR

Area under the log_{10} viral load curve will be computed, out to each of Days 5, 7 and 14, and summarized using descriptive statistics. AUC will be derived using the trapezoidal rule and consider actual study day (per Section 6.7.2) as time. The analysis will also be carried on subgroups of baseline viral load (<median, >=median).

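### Change from baseline in SARS-CoV-2 RNA is only tabulated by arm; the SAP should pre-specify an exploratory, baseline-adjusted difference from placebo with a 95% CI

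*SAP*

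**What the plan says.** The exploratory objective in SAP 3.1.3 is comparative: "The antiviral activity of BEM compared with placebo". Protocol section 2 lists the same objective.

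For the by-visit endpoint, SAP 8.8 states that viral RNA and its change from baseline "will be summarized at each scheduled time point by descriptive statistics", on the log10 scale, together with the number and percentage non-detectable. SAP 6.1 explains what such a summary is: "Descriptive summaries will be tabulated by treatment group", meaning n, mean, SD, quartiles and range for each arm.

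Baseline viral load enters in two places. It is a listed baseline characteristic ("SARS-CoV-2 RT-PCR viral load at baseline", SAP 7.4). It also defines a median split: "The analysis will also be carried on subgroups of baseline viral load" (SAP 8.8). It is not used as a covariate.

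Protocol 8.3.3 makes description the default for the additional antiviral endpoints and leaves any further exploratory analysis to the SAP. The SAP adds none for change from baseline.

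**The concern.** The objective asks how BEM compares with placebo, but this endpoint has no planned quantity that answers it. Readers will subtract one arm's mean change from the other's. That step is not pre-specified, carries no interval in the planned output, and takes no account of any baseline difference between the arms.

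The question is live in this program. Protocol 1.2.1 calls the virology trends inconsistent:

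- about 0.5 log10 at Day 7 in a high-risk subgroup of the Phase 2 outpatient study;
- 0.6 log10 at Day 2 in the hospitalized study;
- no meaningful difference in the earlier outpatient Phase 3 study, which randomized 216.

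The present trial is about ten times that size in the supportive-care-only stratum, so its estimate will be looked for whichever way it falls. The combination stratum, which Protocol 1.5 describes as hypothesis-generating, is small enough for chance baseline imbalance to matter.

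**Working it through.** **Which antiviral endpoints get a comparison**

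- Viral load rebound (secondary): primary-endpoint method (SAP 8.7), so a CMH test and common risk difference, odds ratio and relative risk with 95% CIs (SAP 8.6.1).
- Relapse plus rebound (exploratory): compared between arms by the primary method (SAP 8.8).
- Time to cessation of shedding: Kaplan-Meier (SAP 8.8), with the log-rank test from the general rule in Protocol 8.3. This is a test, not an effect in log10 units.
- Change from baseline in viral RNA: by-arm description only. None of the three endpoints above measures the size of the decline. Rebound, for example, is a rise of at least 1 log10 after end of treatment.

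**Numbers per arm**

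The plan gives no precision or power figure for viral load. Its sample size for the primary endpoint reproduces: 1.6% against 4.0%, one-sided 0.025 and 90% power give 991 per arm, or 1982. Then 1982 × 1.055 = 2091 (stated as 2100), and 2100 / 0.95 = 2210. So mITT-S is 2100 / 2 = 1050 per arm. The combination stratum is up to 300, so at most 150 per arm.

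**Assumptions (not in the documents)**

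SD s = 2.0 log10 at baseline and at follow-up, baseline/follow-up correlation r = 0.3 to 0.5 (0.7 also shown), no missing swabs.

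**Formulas**

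- Variance of the raw change: 2s²(1 − r).
- Variance after ANCOVA: s²(1 − r²).
- Ratio of variances: (1 + r)/2, which is 0.65, 0.75 and 0.85 at r = 0.3, 0.5 and 0.7. Interval widths are multiplied by the square roots, 0.81, 0.87 and 0.92.
- 95% half-width: 1.96 × √(variance × 2/n per arm).

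Example at r = 0.3 and n = 1050: raw 1.96 × √(5.6 × 2/1050) = 0.20; ANCOVA 1.96 × √(3.64 × 2/1050) = 0.16.

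| n per arm | r | Raw change (log10) | ANCOVA (log10) |
|---|---|---|---|
| 1050 | 0.3 | 0.20 | 0.16 |
| 1050 | 0.5 | 0.17 | 0.15 |
| 1050 | 0.7 | 0.13 | 0.12 |
| 150 | 0.3 | 0.54 | 0.43 |
| 150 | 0.5 | 0.45 | 0.39 |
| 150 | 0.7 | 0.35 | 0.32 |

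The interval is 13 to 19% narrower at r = 0.3 to 0.5 and about 8% narrower at r = 0.7.

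**Other SDs and missing swabs**

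With the SD of the change itself set anywhere from 1.0 to 2.5, the raw half-width at 1050 per arm is 0.09 to 0.21. If 95% of the combination stratum also qualified (300 × 0.95 / 2, about 142 per arm), it would be 0.23 to 0.58. With 25% of swabs missing (787 per arm) and an SD of change of 2.0, 0.17 becomes 0.20.

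**Chance baseline imbalance**

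A baseline imbalance d moves the raw difference in change by (1 − r)d. At 150 per arm, a 1.96-SE imbalance is 1.96 × 2.0 × √(2/150) = 0.45 log10. The shift is 0.7 × 0.45 = 0.32 at r = 0.3, 0.5 × 0.45 = 0.23 at r = 0.5 and 0.3 × 0.45 = 0.14 at r = 0.7. At 1050 per arm the imbalance is 0.17 and the shift is 0.12 at r = 0.3 and 0.09 at r = 0.5.

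**The case against.** The strongest reply is that this is a declared choice. Protocol 8.3.3 says that such endpoints are described, and Protocol 1.6 gives a reason: nasopharyngeal viral load may be an unreliable marker of activity for a nucleotide antiviral. The protocol and SAP agree with each other, and neither the primary analysis nor type I error is touched. All of that stands. It explains why no test is planned, but exploratory status alone does not explain the missing estimate, because SAP 8.8 formally compares another exploratory endpoint, relapse plus rebound.

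A reader might infer that the antiviral objective gets no estimate at all. The documents do not support that. Rebound is the named secondary antiviral endpoint and has a risk difference with CI inside the testing sequence (SAP 8.5), and the other comparisons are listed above.

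A reader might also infer that the trial could not show or rule out an effect on viral load. That fails too. The planned n, mean and SD give an unadjusted difference and interval, and randomization protects that difference from systematic bias. In mITT-S its half-width of 0.17 to 0.20 is already well below 0.5 log10. Adjustment there saves only about 0.02 to 0.04.

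Three further cautions stand:

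- Baseline viral load is not available for everyone. SAP 6.5.4 provides for a missing baseline sample, and SAP 6.6 allows a baseline up to 4 hours after the first dose.
- Baseline is not ignored altogether. It is tabulated by arm and used in the median split, though neither yields an adjusted difference.
- The imbalance example is a 1-in-20 event, in a stratum whose size is only an upper limit.

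**Conclusion.** The point holds in a limited form. Change from baseline in viral RNA has no pre-specified between-arm estimate, CI or baseline adjustment. An unadjusted difference could be derived afterwards, but with less precision and with exposure to chance baseline imbalance.

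In mITT-S the loss of precision is small in absolute terms. It matters more in the combination stratum, where the half-width would fall from 0.45–0.54 to 0.39–0.43 log10, and where a 1-in-20 imbalance could shift the raw difference by 0.23 to 0.32 log10, about half of the 0.5 to 0.6 log10 differences that the protocol cites.

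These sizes rest on the assumed SD of 2.0 log10, equal SDs at both times, r of 0.3 to 0.5 and complete swabs. Equal SDs are doubtful at late visits, where SAP 6.8.4 sets every non-detected result to 249. The structural finding, that no estimate is specified, needs none of these assumptions. This is a low-cost improvement to an exploratory analysis. It is not a contradiction between the documents or a threat to the trial's main conclusion.

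**What to change.** In SAP 8.8, keep the descriptive tables and add the following:

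- At Days 3, 5, 7 and 14, report the BEM minus placebo difference in mean change in log10 viral load with a 95% CI, separately in mITT-S and mITT-C.
- Take it from a repeated-measures model (baseline log10 viral load, age, region, visit, treatment-by-visit) or from an ANCOVA at each visit with baseline log10 viral load, age and region.
- Label it exploratory and outside the testing sequence of SAP 8.5.
- Read it beside the proportion non-detectable at late visits, where many values may be substituted at the floor.

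The cost is a few lines of SAP text and one model per stratum, with no new data. The small downside is that a model for means uses the floor-substituted values at those late visits.

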8.9. Summary of Reasons for Efficacy Non-Evaluability/Exclusion from Efficacy Analyses

Reasons for exclusion from mITT populations will be tabulated. Categories include did not receive study drug and did not have ≥ 1 positive SARS-CoV-2 result through Day 5 (from central testing on NP swab samples).

9.

Atea Pharmaceuticals, Inc. Statistical Analysis Plan – AT-03A-017

SAFETY AND TOLERABILITY

9.1. **Overall Summary of Tolerability**

All adverse events will be coded according to the Medical Dictionary for Regulatory Activities (MedDRA) and will be summarized by treatment group for the safety population. Only treatment-emergent adverse events (TEAEs) will be summarized. Treatment-emergent adverse events are those with start date/time within the treatment period, defined as the time from first study drug administration to Day 29. Events that occur after Day 29 with relationship to study drug recorded as 'related' will also be considered treatment-emergent. If the AE onset date is missing or partial, the conventions described in Section 6.8.3 will be used to determine if the event is treatment-emergent.

Adverse event severity will be graded according to the Division of AIDS (DAIDS) Table for Grading the Severity of Adult and Pediatric Adverse Events, Version 2.1 dated July 2017⁶.

An overall summary of TEAEs will be presented and include tabulations (number and %, unless otherwise indicated) for the following:

- Subjects with at least one TEAE, overall and by worst grade
- Total number (number only) of TEAEs
- Deaths
- Subjects who discontinued study due to a TEAE
- Subjects who discontinued treatment due to a TEAE
- Subjects with a treatment-related TEAE resulting in treatment discontinuation
- Subjects with a treatment-emergent serious adverse event (SAE)
- Subjects with a treatment-related SAE
- Subjects with a treatment-related TEAE, overall and by worst grade
- Subjects with a COVID-19 related TEAE
- Subjects with a non-COVID-19 related TEAE

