6. STUDY PROCEDURES AND GUIDELINES

Study-specific assessments and the study schedule are summarized in Table 1. An "X" indicates when the assessments are to be performed.

When feasible, visits may be conducted remotely (eg, via telephone or telemedicine), in clinic, or at home.

If possible, screening and Day 1 will occur on the same day, as soon as eligibility is confirmed. Assessments need not be conducted twice if screening/Day 1 occur on the same day. Screening/Day 1 assessments should occur prior to first dose of study drug. Dosing should occur within 24 hours of screening.

The Day 60 visit can be a telephone contact.

All subjects who prematurely discontinue study treatment should be encouraged to remain in the study and maintain the same protocol schedule and assessments as described in Table 1. This will allow for continued subject follow-up for key outcome data. Subjects who prematurely discontinue the study [prior to Day 29 (primary study period)] and are unable to maintain the same protocol schedule should complete early termination (ET) assessments at the time of study discontinuation.

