7. ADVERSE EVENTS

7.1. **Definitions**

An AE is defined as any untoward medical occurrence in a subject administered a medicinal product(s) and which does not necessarily have to have a causal relationship with this treatment. An AE can therefore be any unfavorable and unintended sign (for example, an abnormal laboratory finding), symptom, or disease temporally associated with the use of a medicinal product(s), whether or not considered related to this medicinal product(s).

A suspected adverse reaction is any AE for which there is a reasonable possibility that the drug(s) caused the AE. 'Reasonable possibility' means there is evidence to suggest a causal relationship between the drug(s) and the AE. A suspected adverse reaction implies a lesser degree of certainty about causality than adverse reaction, which means any AE caused by a drug(s).

An AE may be:

- A new illness
- Worsening of a previous chronic illness or a concomitant illness
- An apparent adverse effect of the study medication(s) on safety-related laboratory tests. This observation could include a clinically-significant abnormal laboratory value or a significant shift from baseline (though still within normal range) which the clinical investigator or qualified designate considers to be clinically significant

Surgical procedures themselves are not AEs. They are therapeutic measures for conditions that required surgery. The condition for which the surgery is required is an AE, if it occurs or is detected during the study period. Planned (elective) surgical measures and the conditions(s) leading to these measures are not AEs, if the condition(s) was (were) known before the start of study treatment. In the latter case, the condition should be reported as medical history.

An SAE or reaction is any untoward medical occurrence that at any dose:

- Results in death
- Is life-threatening
- Requires inpatient hospitalization or prolongation of existing hospitalization
- Results in persistent or significant disability or incapacity (defined as a substantial disruption of a person's ability to conduct normal life functions)
- Is a congenital anomaly or birth defect
- Is an important medical event that may jeopardize the subject or may require intervention to prevent one of the other outcomes listed above (according to medical judgment of the qualified investigator)

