7.2. Routine Reporting

For the purposes of this study, non-serious AEs and SAEs will be recorded in the eCRF from the time of informed consent through Day 29 (the primary study period). SAEs will be recorded through Day 60.

During these periods, all AEs spontaneously reported by the subject, observed by the clinical staff, or elicited by general questioning will be recorded and reported in the eCRF.

Any AE which remains unresolved as of the last visit will require follow-up until the AE has been resolved, a reasonable explanation for its persistence found, or is deemed chronic or stable by the investigator. It is the investigator's responsibility to ensure subjects experiencing AEs receive appropriate follow-up, treatment where required, and that every action is well documented.

Classification will be performed by System Organ Class (SOC) and preferred term using the Medical Dictionary for Regulatory Activities (MedDRA).

In general, AEs occurring secondary to other events (eg, clinical sequelae or a cascade of events) should be identified by their primary cause. For example, if severe vomiting is known to result in dehydration, it is sufficient to record only vomiting as an SAE or AE in the eCRF. However, medically significant AEs occurring secondary to an initiating event that are separated in time should be recorded as independent events on the eCRF.

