7.3. Serious Adverse Event Reporting

Clinical sites must notify of any SAE, without regard to causality, within 24 hours after becoming aware of its occurrence. Any non-serious AE which worsens and eventually meets the criteria for an SAE must also be reported as a new SAE.

Information regarding SAEs will be transmitted to celevate using the Serious Adverse Event form in the electronic data collection tool, which must be completed by a member of the investigational site staff within 24 hours. This form should include a clearly written narrative describing diagnostic terms, signs, symptoms, and treatment of the event; diagnostic procedures; as well as any relevant laboratory data and an assessment of the potential causal relationship between the event and the investigational product(s). Information not available at the time of the initial report (eg an end date for the AE, laboratory values received after the report, or hospital discharge summary) must be documented. All follow-up information must be reported as soon as the relevant information is available.

If the electronic system is unavailable, then the site will use the paper SAE data collection tool and transmit to collection within 24 hours by one of the following methods:

Email: PPD	
Fax:PPD	

The site will enter the SAE data into the electronic system as soon as it becomes available.

Contact information for the Sponsor's physician is also listed below, should the sites need to contact the Sponsor to discuss any medical, safety related questions, or SAEs:

PPD Atea Pharmaceuticals, Inc.
Telephone PPD
Email: PPD

An unlisted (unexpected) SAE is one in which the nature or severity is not consistent with the applicable product reference safety information (RSI). For investigational product(s), the expectedness of an SAE will be determined by whether or not it is listed in the RSI within the Investigator's Brochure(s). Investigators will be notified, and the Investigator's Brochure will be updated, if any new pattern of AEs or laboratory abnormalities is found to be related to BEM dosing.

The start date of an SAE reported on the Serious Adverse Event form must be the same as the start date of the corresponding AE documented on the eCRF. If a change in severity is noted for the existing AE, it must be recorded. If a worsened AE meets the criteria for an SAE, the start date of the SAE must be the same as the start date of the worsened AE.

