8.3.4. Safety Analyses

The treatment-emergent period for safety analyses is the time from first study drug administration to Day 29. All lab summaries will be presented by treatment group. Proportions of subjects experiencing treatment-emergent SAEs, AEs, and AEs resulting in treatment discontinuation will be summarized. Adverse event terms will be coded using MedDRA thesaurus terms. Treatment emergent events will be summarized by MedDRA SOC and preferred term, overall and by severity. For subjects experiencing an event with varying severity, the highest grade will be used in the summaries. Deaths and cause of death will be summarized.

Laboratory and vital sign data will also be summarized. Where applicable, laboratory abnormalities will be graded in accordance with the DAIDS severity scale. Shift tables for treatment emergent laboratory abnormalities will be presented.

Study treatment exposure (such as treatment duration and total dose received) will be summarized with descriptive statistics.

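### SAP 9.1 counts an adverse event as treatment-emergent by its start date alone, so a pre-dose event that worsens on study drug can drop out of the TEAE tables

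*SAP*

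**What the plan says.** SAP 9.1 restricts the adverse event tables: "Only treatment-emergent adverse events (TEAEs) will be summarized". It then gives the entry rule: "Treatment-emergent adverse events are those with start date/time within the treatment period", with the period running from first dose to Day 29. Events after Day 29 also count if recorded as related to study drug. Missing or partial onset dates are referred to SAP 6.8.3. There is no provision for an event that was already present at first dose and then got worse.

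Protocol 8.3.4 sets the same period: "The treatment-emergent period for safety analyses is the time from first study drug administration to Day 29". It also has no worsening provision, so the two documents agree.

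Collection begins earlier than the treatment-emergent period. Protocol 7.2 has events recorded "from the time of informed consent through Day 29", and Protocol 6 adds: "Dosing should occur within 24 hours of screening". Screening and Day 1 are to fall on the same day if possible.

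On changes in an event already recorded, Protocol 7.3 says: "If a change in severity is noted for the existing AE, it must be recorded". For events that turn serious it says: "Any non-serious AE which worsens and eventually meets the criteria for an SAE must also be reported as a new SAE". Protocol 7.1 includes among possible adverse events: "Worsening of a previous chronic illness or a concomitant illness".

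**The concern.** A rise in grade after first dose is a possible drug effect, and it is one of the things that a TEAE table exists to compare between arms. A rule that looks only at onset classifies an event by when it began, even if the clinically important part came later on treatment. A mild complaint noted a few hours before the first tablet that becomes grade 3 on Day 3 would be handled as a pre-treatment event.

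What is at stake is limited to safety reporting. No efficacy result, type I error or power figure depends on this rule. The question is whether a few clinical events would be seen only in a listing and not be compared between arms.

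**Working it through.** The plan gives no figure to reproduce, so the check is mainly a reading of the rules side by side, followed by simple arithmetic for scale.

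**Step 1: apply the rule to one case.** An event starts after consent and before first dose at grade 1, reaches grade 3 on Day 3, stays non-serious and is kept as one record.

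- SAP 9.1: the start is before first dose, so it is not a TEAE. The route for related events after Day 29 does not apply.
- SAP 6.8.3: a wholly missing start date counts as treatment-emergent, and a date known only to month and year is set no earlier than treatment start. Neither rule reaches an event with a full pre-dose date.
- SAP 9.2: the tables by preferred term, maximum severity and relatedness are built on TEAEs, so the event is absent from them.
- Protocol 8.3.4: an event of varying severity is shown at its highest grade. This decides which grade is shown, not whether the event enters the table, and it fits with a single record that keeps its original start date.

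If the site instead opens a new record dated at the worsening, the event is counted.

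**Step 2: do the documents require that new record?** For a non-serious change, Protocol 7.3 requires only that the change be recorded. It does not ask for a new entry or a new start date.

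For an event that becomes serious, a new SAE report is required. However, the same section ties the SAE start date to that of the worsened adverse event, and this can be read in two ways:

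- If it means the date of worsening, the SAE is dated on treatment and is counted.
- If it means the original onset, the SAE carries a pre-dose date and fails the SAP 9.1 test.

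**Step 3: what else would show the event?**

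- Listings of all safety data (SAP 6.1).
- Laboratory shifts from baseline to worst grade (SAP 9.5).
- Vital-sign changes and markedly abnormal values (SAP 9.6).
- Treatment discontinuation by reason and arm in the ITT population, whatever the TEAE status (SAP 7.1).

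What is left is chiefly clinical events that are neither laboratory nor vital-sign findings.

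**Step 4: scale, using planned arm sizes at 1:1** (Protocol 8.5: 2210 supportive-care-only subjects, up to 300 combination subjects).

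- Arm sizes: 2210/2 = 1105; 300/2 = 150 at most.
- One omitted subject: 1/1105 = 0.09 percentage points; 1/150 = 0.67 percentage points.
- Common-event table of SAP 9.2 (5% in any arm): 0.05 × 1105 = 55.25, so 56 subjects; 0.05 × 150 = 7.5, so 8 subjects.

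The number of events affected cannot be derived from the documents, and none is assumed.

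**The case against.** The strongest reply is that Protocol 7 may already close the gap. An event still present at first dose could be called a concomitant illness, whose worsening Protocol 7.1 treats as an adverse event in its own right. The dating sentence in Protocol 7.3 could also mean that a worsened event has its own start date. On that reading sites would open a new record and SAP 9.1 would count it. Whether they do so depends on eCRF design and completion instructions, which are not in the documents.

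This narrows the point without removing it. Protocol 7.1 says what may be an adverse event. It does not tell sites to re-enter one already on record. The Protocol 7.3 sentence is ambiguous and concerns events that become serious. A TEAE definition should not depend on an unstated data-entry habit.

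The reply is also right that the affected set is very small. The event must start in a window of at most about 24 hours, often within the same day. It must not be a symptom captured at screening as pre-existing, and it must then worsen without a new record. The backups in SAP 6.1, 7.1, 9.5 and 9.6 are real, though partial.

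Three stronger readings are tempting, and the documents support none of them:

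- **A conflict between SAP and protocol.** There is none, because Protocol 8.3.4 uses the same period and has the same silence on worsening.
- **A bias for or against bemnifosbuvir.** The same rule applies to both blinded arms, and no direction can be derived.
- **A materially understated count of discontinuations for adverse events.** SAP 7.1 tabulates discontinuation by reason and arm independently of TEAE status, and no number of affected subjects is available.

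**Conclusion.** The point holds in a narrow form. As written, SAP 9.1 leaves out of the TEAE, maximum-severity and related-TEAE tables a non-serious clinical event with a dated onset between consent and first dose that rises in grade on drug, unless the site opens a new record. The documents do not clearly require that record. Events that become serious are not securely covered either, because of the ambiguous dating rule.

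The size is very small. Common-event rows would hardly move. Only sparse rows, such as higher-grade or related events, could change visibly, and mainly in the combination stratum, which is presented separately (SAP 6.4). This rests on two assumptions: planned enrolment is reached, and at least some sites keep a worsening event as one record. The second cannot be tested from the documents. It is an optional improvement.

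**What to change.** In SAP 9.1, define a TEAE as an adverse event that starts, increases in severity or becomes serious on or after first study drug through Day 29. Keep the existing rule for related events after Day 29. For events that qualify by worsening, count the maximum grade reached after first dose. Where worsening of a pre-dose event is recorded without a date, treat it as treatment-emergent, in line with how SAP 6.8.3 treats a wholly missing start date.

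The cost is one sentence and a small programming rule. SAP 2 lets the document evolve until it is finalized before unblinding. After that, the change would have to be reported as a deviation in the clinical study report. The drawback is that the rule depends on how the eCRF dates severity changes, which the documents do not show. The fallback may also admit a few events that worsened before first dose, though under the same rule in both blinded arms.
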